- 2) To compare the efficiency of the chemo-mechanical method (BRIX3000[®], Carie-Care[™]) versus the conventional surgical method in caries removal of primary molar teeth in vivo.
- 3) To compare the pain experienced by children during dental treatment with the chemo-mechanical method (BRIX3000[®], Carie-Care[™]) versus the conventional surgical method in caries removal of primary molar teeth in vivo.

HYPOTHESIS

The null hypothesis for this research will be as follows:

There is no difference in the efficacy, efficiency and pain experienced between chemo-mechanical caries removal agents (Brix3000[®]), (Carie-CareTM) and the conventional surgical methods in primary molars.

RESEARCH MATERIALS AND METHODS

This study will be carried out at King Abdulaziz Dental University Hospital (KADUH) and at Microbiology Research Laboratory in the Faculty of Pharmacy, King Abdulaziz University in Jeddah, Saudi Arabia to evaluate the efficacy, efficiency, pain experienced by children with the use of the chemo-mechanical method (BRIX3000[®]) and (Carie-Care[™]) versus the conventional surgical method in primary molars.

Materials:

Ethical Approval

The study was approved by the “Research Ethics Committee” at Faculty of Dentistry, King Abdulaziz University (KAU), under approval number 107-06-19.

Informed Consent

Written informed consent will be received from the parents or the guardians of the children after explaining the research procedures to them.

Subjects (sampling)

The study sample will consist of healthy and cooperative children between the ages of 4-9 years with bilateral open occlusal carious lesions in primary molars, who will attend as outpatients to the Department of Pediatric Dentistry at KADUH during the period from October 2019 to October 2020.

Inclusion criteria:

- Healthy and cooperative patients of age group 4-9 years.
- Primary first/second molars with open occlusal carious lesion having moderated depth and clinically visible brownish color softened dentin.
- No clinical signs or symptoms of pulp degeneration, such as tenderness to percussion and history of sinus tracts or swelling. Intraoral periapical radiographs with lesions having radiolucency extending into, but only confined to dentin.

Exclusion Criteria:

- Patients with any major and minor systemic illness.
- Uncooperative patients that necessitate pharmacological dental treatment.

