- 9) Inoculation loop.
- 10) Blood agar plates “Schaedler agar”
- 11) GC Fuji IX GP®.
- 12) A Stop Watch.

Methods:

Study design

Experimental, randomized controlled clinical trial with two-arm parallel groups and bilateral design following the “Consolidated Standards of Reporting Trials (CONSORT,2010)” statement (Fig.3).

Randomization

Since bilateral technique will be utilized in both parallel groups, it was decided to start on the right side irrespective of the method assigned by randomization. To control the variable of the side favored by the clinician, the researchers will make sure that each side is treated evenly by both methods using block randomization. Before recruiting participants, 60 sealed envelopes containing the randomization results will be arranged, sealed and mixed blindly in a box. Each envelope represents a block of the two contralateral teeth. The envelopes will be numbered blindly from 1 to 60. Each envelope will be opened immediately before starting the procedure on the right side.

[figure not shown]

Figure 3: Flow diagram of the Study

Clinical Procedures

The degree of dental destruction will be clinically determined by using a dental probe. Only open occlusal cavities with brown and softened dentin with broadly comparable depth exhibiting frank moderate cavitation will be chosen “severe decay, stage 5, ICDAS [International Caries Detection and Assessment System]” (Ismail et al., 2007, Dikmen, 2015). The depth of caries progression will be confirmed with an intraoral periapical radiograph such that radiolucency did not involve the pulp.

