To assess the efficacy of caries removal in all groups, the outer surface of the decayed lesion will be washed with sterile normal saline (5 mL) to avoid contamination of plaque bacteria before taking the sample. The first sample will be taken from superficial carious lesion with the aid of a sterile sharp spoon excavator (Size #4; Nordan Manufacturing Inc., [name]). After completing caries removal, the cavity will be washed with sterile normal saline (5 mL) and dried with a sterile cotton pellet. A second sample of dentin will be taken from different sites of the cavity including the walls and floor using a sterile sharp spoon excavator (Size #4; Nordan Manufacturing Inc., [name]). The first and second samples will be collected in screw cap sterile vials containing 1 ml of isotonic saline for microbiological evaluation. Following decay elimination by both techniques, cavities will be filled using Glass Ionomer restoration (GC Fuji IX GP[®]) according to manufacturer’s instructions. For Microbiological cultivation and evaluation, dentin samples of all groups will be processed in the Advanced Techniques Laboratory in Dental research within 2 hours of collection. The samples will be vortexed for 30 sec to remove the microorganisms from dentin. The samples will be then regularly watered to obtain a 10^4 , and a sterile loop full of sample (0.1 ml) will be collected and cultured with aseptic technique onto blood agar plates (Schaedler agar) by streaking method. Then, the plates will be incubated aerobically at 35°C for 24 hours. Using

colony counter, the total viable count (TVC) will be obtained and expressed as colony forming units “CFU” per ml of sample.

To determine the efficiency of caries removal in all groups, time will be recorded in seconds by using a stopwatch from the beginning of caries removal till the cavity is certain to be caries-free.

To assess the pain experienced throughout caries removal in all groups, the “Wong-Baker FACES® Pain Rating Scale” (Wong & Baker, 1988) will be utilized (Fig. 4).

Dental treatment will be accomplished according to the following steps:

- Local anesthesia will be used for all groups.
- Rubber dam isolation will be used for all groups.
- Caries removal will be done utilizing one of the 3 techniques as follows:

The Control Group: Caries removal using “conventional drilling method”

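### As written, the envelope may be opened before the right tooth's baseline dentin sample is taken; opening it after that sample is a cheap, partial improvement

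*Combined protocol and SAP*

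**What the plan says.** The Randomization section sets the moment of disclosure: "Each envelope will be opened immediately before starting the procedure on the right side". It also says that "Each envelope represents a block of the two contralateral teeth", that "60 sealed envelopes containing the randomization results will be arranged, sealed and mixed blindly in a box", and that "it was decided to start on the right side irrespective of the method assigned by randomization". One opening therefore reveals the method for both teeth of a child. The section does not define where the procedure begins.

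The Clinical Procedures section describes the baseline: "The first sample will be taken from superficial carious lesion with the aid of a sterile sharp spoon excavator". The scraping goes into a vial holding 1 ml of saline and is reported as CFU per ml. No weight, volume or number of strokes is given, and the site is specified only as the superficial lesion. A second scraping is taken from several parts of the cavity after caries removal. The plan does not say who takes either sample, whether that person is unaware of the method, or whether the first sample comes before or after the envelope is opened.

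The same section lists steps ahead of caries removal: "Local anesthesia will be used for all groups" and "Rubber dam isolation will be used for all groups". The Brix3000 technique text further on says otherwise, describing work with no anesthetic and with cotton rolls for isolation.

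**The concern.** Objective 1 compares how far each method lowers the bacterial count, so the first sample enters the result as directly as the second. Dentin is scraped by hand into a fixed volume and is not weighed, so more dentin in the vial gives a higher CFU per ml. If the person scraping knows the method, the baseline, and with it the apparent decrease, can move with no change in what is left in the cavity. The Expected Findings section says the results may favor Brix3000, so a possible direction is already on record.

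A second, smaller matter is that there are 60 envelopes for 60 children and no stated allowance for losses. A child who cannot go on after the opening has used an envelope. A child who cannot go on before it need not.

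**Working it through.** **1. The plan's counts.** From the Sample Size and Randomization sections: 60 control + 30 Brix3000 + 30 Carie-Care = 120 teeth, and 60 envelopes × 2 teeth = 120. These agree. The 30 per group cannot be re-derived because no effect size or SD is given, but the timing of the opening does not depend on it.

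**2. When is the method known?** The answer turns on one undefined word.

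- *Broad reading.* The first sample is described under the heading Clinical Procedures, and the Brix3000 text uses the word in a sense that includes anesthesia and isolation. The opening then precedes the sample and the preparation.
- *Narrow reading.* The Brix3000 text also uses the word for a repeat round of gel and excavation. If it means caries removal only, the opening could follow the sample.

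The broad reading is the more natural one for the Randomization sentence. Neither reading is stated.

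**3. Which samples does the timing affect?** Each child has one right tooth, treated first, and one left tooth.

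| Sample | Number | Method known as written | Method known if opened after right first sample |
|---|---|---|---|
| Right baseline | 60 | possible | no |
| Left baseline | 60 | yes | yes |
| Second sample | 120 | yes | yes |

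The change protects up to 60 of 120 baselines, or 60 of 240 samples in all (25%).

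**4. What could extra dentin do?** Assume the count is proportional to the dentin scraped. Let B be the baseline count, P the second count and R = log10(B) − log10(P). If knowledge of the method multiplies the dentin scraped at baseline by k, R rises by log10(k):

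- k = 1.25: log10(1.25) = 0.10
- k = 1.5: log10(1.5) = 0.18
- k = 2: log10(2) = 0.30

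The values of k are assumptions. The log scale is chosen for illustration; the plan names no transformation.

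Suppose the shift occurs only in test teeth, and half of the test teeth are on the right, as the plan's aim of treating each side evenly implies. Protecting the right side then cuts the average shift at k = 2 from 0.30 to 0.5 × 0.30 = 0.15.

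**5. What could a shift do to a test?** Take 30 pairs, a paired t-test at two-sided 0.05, no true difference, and an average shift of b SDs of the within-child difference. The statistic is noncentral t with 29 degrees of freedom and noncentrality b × √30. The rejection rates are:

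- b = 0: 5%
- b = 0.1: noncentrality 0.55, 8%
- b = 0.2: noncentrality 1.10, 19%
- b = 0.3: noncentrality 1.64, 36%

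The documents give no value for b, so these rates show sensitivity and do not estimate the error in this trial.

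**6. Losses after opening.** Each child lost removes one pair: 1/30 = 3.3% of the pairs in that comparison.

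**The case against.** The strongest reply is that the concern rests on one undefined word. On the narrow reading the opening may already follow the sample, and the study flow diagram, which is not available here, may bear on the order. This stands as far as it goes: early knowledge at the right tooth is something the text permits and does not prescribe. It does not remove the point, because no available text places the sample first.

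A second reply is that the remedy is small. The left baselines and every second sample stay exposed, and the underlying weakness is unstandardized scraping by someone who may know the method. This also stands, and it is why a fixed sampling instruction belongs with the reordering.

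A third reply is that opening envelopes at the chair already protects concealment up to enrolment. That is right, and concealment at enrolment is not in question here.

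Several stronger readings are tempting, but the documents do not support them:

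- *Children will be excluded as uncooperative after allocation.* The criterion "Uncooperative patients that necessitate pharmacological dental treatment" is listed with eligibility and concerns children who need pharmacological management. No text applies it after the opening. The listed exclusion that does operate after allocation is failure to complete the second session, and this change leaves it untouched.
- *All preparatory steps are common, so all can precede the opening.* The list of treatment steps says so, but the Brix3000 text contradicts it on anesthesia and isolation.
- *Losses break the within-child comparison.* A lost child takes both teeth out, so the remaining pairs are intact.
- *The plan predicts that Brix3000 will win.* It says only that findings may show this.

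**Conclusion.** The point holds as a cheap improvement. The envelope instruction does not keep the method from the person taking the right tooth's first sample, and that sample is hand-scraped, of unstandardized amount, and anchors objective 1. Up to 60 of 120 baselines are affected unnecessarily.

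The size of any bias is unknown. The 0.30 log10 figure assumes that twice the dentin is scraped and that the count is proportional to dentin; the rejection rates assume a shift that the documents do not give. A reader might infer that the trial's bacterial result is biased. The documents show an avoidable opportunity for bias and nothing more. Each loss after opening costs 3.3% of the pairs in one comparison, which is a loss of precision, with a possible change in which children are analyzed.

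**What to change.** Replace the sentence in the Randomization section with:

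> Each envelope is opened after eligibility of both teeth is confirmed and the first sample of the right tooth is in its vial, immediately before the first step that depends on the method.

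Add that a child who cannot go on before that point does not use an envelope.

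Add to Clinical Procedures one sampling instruction, with sites and amount fixed in advance, for first and second samples on both sides. This covers the 60 left baselines and 120 second samples that the reordering cannot protect.

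The general list of treatment steps and the Brix3000 text must be reconciled on anesthesia and isolation before deciding whether those steps can also precede the opening. This review takes no position on which text should stand.

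Cost: the reordering changes no sample size, intervention or analysis, and materials for all methods must be ready at the chair before the envelope is opened. The sampling instruction takes a short text and some operator training.

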The disadvantages accompanied with the use of the conventional surgical method of caries removal has been overcome by the use of “chemo-mechanical caries removal method”. “Chemo-mechanical caries removal” is one of the minimally invasive techniques that found to be less painful, less destructive and more accepted by children (Goomer et al., 2013, Soni et al., 2015). In addition to these advantages, the research holds clinical significance as a novel agent for “chemo-mechanical caries removal” (BRIX3000[®]) by the laboratory Brix Medical Science. It has been released recently in the dental market in 2015. It is a papain-based gel derived from leaves latex and fruits of green papaya (Carcia Papaya) that works as chemical debridement. It is for atraumatic caries removal with unique technology Encapsulating Buffer Emulsion (EPE) (Felizardo et al., 2018). This technology, according to the manufacture, provides the product with:

1. Proteolytic enzymatic activity that differs than previous products (Carie-Care) in the amount of papain used (3,000 U/mg in a concentration of 10%).
2. Perfect pH that solidifies the enzymes and set them free instantly on the collagen through its proteolytic activity.
3. Stable in room temperature with no need to be refrigerated with increased its shelf-life up to 48 months.
4. Increased enzymatic selectivity to damaged collagen.
5. Reduced time needed for removing the damaged dentinal tissues.
6. Enhanced the antifungal, antibacterial, and antiseptic ability.
7. Increased roughness to the cavity floor that favored better adhesion of the restoration.

By reviewing the literature, there are limited studies concerning its implementation in the area of pediatric dentistry. Clinical and microbiological studies are needed to confirm

manufacturer's claims by comparing this novel chemo-mechanical agent (BRIX3000[®]) and the previously-available chemo-mechanical agent (Carie-Care[™]) to the conventional surgical method for caries removal. Therefore, the purpose of this research is to perform clinical and microbiological evaluation of caries removal using these three different methods of caries removal in primary molars.

RESEARCH OBJECTIVES

- 1) To compare the efficacy of the chemo-mechanical method (BRIX3000[®], Carie-Care[™]) versus the conventional surgical method in decreasing the cariogenic bacteria in dentine caries of primary molar teeth in vivo.

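### Bacterial counts are reported per ml of suspension while the dentin in each vial is only loosely controlled and never recorded, so the bacterial reduction is confounded with sample mass

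*Combined protocol and SAP*

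**What the plan says.** Objective 1 (Research Objectives) is to compare the methods "in decreasing the cariogenic bacteria in dentine caries of primary molar teeth in vivo". The count described under Clinical Procedures is the only bacterial measure in the protocol.

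- **Before treatment:** "The first sample will be taken from superficial carious lesion with the aid of a sterile sharp spoon excavator".
- **After treatment:** "A second sample of dentin will be taken from different sites of the cavity including the walls and floor", with the same size #4 excavator.
- **Carrier:** "The first and second samples will be collected in screw cap sterile vials containing 1 ml of isotonic saline for microbiological evaluation".
- **Plating:** "a sterile loop full of sample (0.1 ml) will be collected and cultured".
- **Outcome:** "the total viable count (TVC) will be obtained and expressed as colony forming units", with the denominator given as "per ml of sample", that is, per ml of suspension.

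No weight, volume, number of scoops or number of sites is given for either sample. The Armamentarium & Equipment list has no balance. Statistical Analysis names paired and independent t-tests, or Wilcoxon and Mann-Whitney tests, with no adjustment for sample amount. Research Limitations does not mention the matter.

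**The concern.** With a fixed 1 ml carrier, twice as much dentin at the same bacterial density gives twice the CFU/ml. The count therefore measures two things at once: how contaminated the dentin is, and how much of it reached the vial. Only the first is of interest for Objective 1.

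Two comparisons are exposed, to different degrees.

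- **Pre-post reduction.** The two samples come from different sites and different tissue: soft superficial caries first, then the walls and floor of an excavated cavity. Equal yield cannot be assumed.
- **Between methods.** The second sample is taken from whatever surface each method leaves. The protocol's opening section says that the chemo-mechanical approach spares caries-affected dentin which the conventional approach also removes, so the residual surfaces may differ. Whether scrape yield then differs is an inference. If it does, the difference arises after treatment, and neither randomisation nor the split-mouth pairing balances it.

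**Working it through.** The documents contain no figure for dentin mass, CFU variability or an expected bacterial effect, so there is no plan figure to reproduce. The only sample-size statement concerns an anxiety score. Every quantity below that is marked as assumed is illustrative.

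**Inputs from the protocol.** Carrier volume 1 ml; 60 control teeth, 30 Brix3000 teeth and 30 Carie-Care teeth in 60 children, hence 30 within-child pairs for each chemo-mechanical versus conventional comparison; significance level 0.05 (taken as two-sided, because sidedness is not stated).

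**Step 1: what the outcome measures.**

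CFU/ml = (CFU per mg × mg in vial) / 1 ml

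A mass ratio r therefore shifts log10 CFU/ml by log10(r):

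- r = 1.5: 0.18
- r = 2: 0.30
- r = 3: 0.48

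**Step 2: effect on the pre-post reduction.** With CFU per mg unchanged, a second sample of half the mass shows an apparent reduction of 1 − 0.5 = 50% (0.30 log10). A quarter of the mass shows 1 − 0.25 = 75%.

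**Step 3: systematic mass difference between methods (assumed).** Suppose there is no true difference in CFU per mg, and that the second-sample mass differs by ratio r between methods. For a paired t-test on log10 values, the noncentrality is log10(r) / SD × √30 with 29 degrees of freedom, where SD is the assumed standard deviation of the within-pair difference. For r = 2 and SD = 0.5 this is 0.301 / 0.5 × 5.48 = 3.30. The probability of p < 0.05 is:

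| Assumed mass ratio | SD 0.5 | SD 0.75 | SD 1.0 |
|---|---|---|---|
| 1.5 | 0.46 | 0.24 | 0.15 |
| 2 | 0.89 | 0.57 | 0.36 |

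The nominal rate is 0.05.

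**Step 4: mass varies only at random (assumed).** For log-normal mass with coefficient of variation CV, the SD of log10 mass is s = √ln(1 + CV²) / ln 10. A between-method difference in reductions uses four independent samples, so it gains an SD of √4 × s = 2s. Take an assumed base SD of 0.5 and an assumed true difference of 0.4 log10 with 30 pairs. Power without mass variation is 0.99.

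| CV | 2s | Total SD = √(0.5² + (2s)²) | Power |
|---|---|---|---|
| 30% | 0.25 | 0.56 | 0.96 |
| 50% | 0.41 | 0.65 | 0.91 |
| 100% | 0.72 | 0.88 | 0.67 |

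**Step 5: is weighing accurate enough?** Mass is the difference of two weighings, so its error SD is √2 × the error of one weighing. For an assumed sample of 2 to 5 mg:

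- 1 mg per weighing gives 1.41 mg, that is 71% of 2 mg and 28% of 5 mg.
- 0.1 mg per weighing gives 0.14 mg, that is 7% of 2 mg and 3% of 5 mg.

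The precision of the balance therefore decides whether normalising to mass helps.

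**The case against.** The strongest defence has four parts.

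1. **Sampling is not uncontrolled.** The excavator size, wash volume, carrier volume and plated volume are the same throughout. Lesions are restricted to one ICDAS stage and broadly comparable depth, and teeth are paired within a child. This stands: control is loose rather than absent. But it fixes the instrument and the lesion at entry, not the amount collected.

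2. **Nothing shows that yield differs by method.** All three techniques are taken to a visual and tactile caries-free endpoint, so the second sample is meant to come from clinically similar dentin. This also stands. A reader might infer that the between-method result will be an artefact of sample mass. The documents do not support that. If mean mass is equal across methods, the comparison loses precision and is not biased, and the loss is modest unless mass varies widely. Even where softer residual dentin yields more, part of the extra count may reflect remaining carious tissue, which Objective 1 is about.

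3. **The rejection probabilities rest on assumptions.** They assume mass ratios, SDs and a roughly normal log10 outcome under a paired t-test. The protocol specifies no log transform and allows rank tests. If the dilution step, which reads unclearly, means a 10^4-fold dilution, one colony from 0.1 ml represents 10^4 / 0.1 = 10^5 CFU/ml. Post-treatment zeros could then be common, and a mass ratio would not act as a clean shift. The percentages are not estimates of this trial's false-positive rate.

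4. **Weighing milligram samples is itself noisy.** This is true at 1 mg precision and largely answered at 0.1 mg, although moisture carried over from the saline wash would still be weighed as dentin.

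None of this touches the pre-post reduction, where the two samples differ in site and tissue by design.

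**Conclusion.** The point holds in limited form. CFU/ml of a fixed suspension, with dentin mass unrecorded, confounds the pre-post reduction with sample amount: halving the mass alone looks like a 50% reduction. For the between-method comparison, the certain consequence of varying mass is lost precision. Bias is possible, in an unknown direction, if residual dentin yields differently by method. The range of 0.89 to 0.36 for a 2-fold ratio shows what such a bias could do under the stated assumptions. It does not say that a 2-fold ratio exists. The matter affects one of three objectives and has no bearing on the stated 30 per group. It merits correction because it is inexpensive to correct and because the mass cannot be recovered once a sample has been processed.

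**What to change.** Weigh each closed saline vial before sampling and again on receipt in the laboratory, on an analytical balance reading to 0.1 mg or better. Record the difference as dentin mass. Define the efficacy outcome as log10 CFU per mg, with CFU/ml as a sensitivity analysis. Do not change how much tissue is removed: setting a quantity to be scraped from a finished cavity would be a clinical decision, and none is proposed here.

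**Cost.** 120 teeth × 2 samples = 240 vials, each weighed twice, or about 480 weighings, plus access to a suitable balance. No patient procedure or extra staff is needed. Some error remains from small samples (about 3 to 7% at 0.1 mg per weighing for an assumed 2 to 5 mg sample) and from carried-over moisture.

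If no such balance is available, restrict the conclusion: state that differences in CFU/ml cannot be separated from differences in the amount of dentin sampled.

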The carious cavity will be treated with Carie-Care™ “Uni-Biotech Pharmaceuticals Private Limited, Chennai, India in collaboration with Vittal Mallya Scientific Research Foundation”. Following the instructions of the manufacturer, the Carie-Care™ gel will be brought to room temperature. The gel will be left in the carious lesion for 60 seconds. At that time, the appearance of the gel will be changed from translucent into cloudy. Then the gel will be removed with moistened cotton pellet and softened carious dentin will be scrapped off using spoon excavator ((Size #2, #3, #4; Nordent Manufacturing Inc., [name]). The process will be redone till consecutive administration of the gel was unsuccessful to turn into cloudy. Decay removal will be verified by probing with dental explorer (visual-tactile clinical criteria).

Statistical Analysis

The statistical assessment will be carried out using Statistical Package for Social Sciences (SPSS, V.20, IBM; Armonk, NY, USA). Analysis of data will be done through measuring *p*-value to determine statistical significance. The level of significance will be set at 0.05 (*p*-value of less than 0.05 was considered statistically significant). Various statistical methods will be used for measuring *p*-value depending whether the data will be normally distributed (parametric) or not normally distributed (non-parametric). For normally distributed data, paired sample t-test and independent sample t-test will be used. For non-normally distributed data, Wilcoxon signed rank test and Mann Whitney U test will be used.

Wong-Baker FACES® Pain Rating Scale

[figure not shown]

Figure 4: Wong-Baker FACES® Pain Rating Scale.

RESEARCH LIMITATIONS

Although, the chemo-mechanical methods cannot eliminate the dental caries completely, it tends to follow the principles of minimal intervention dentistry approaches. The generalization of results is one of the expected limitations of this research.

STRUCTURE OF THE RESEARCH

The research will be divided into several chapters:

- Chapter 1 will represent the introductory note on the state of dental caries among children and treatment approaches that are extensively used by the dentists including different chemo-mechanical agents used.
- Chapter 2 will present the literature review for the study.

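### Only one dilution and one streaked 0.1 ml plate are described for both dentin samples, so low post-removal counts could be lost; how much depends on residual loads the plan does not give

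*Combined protocol and SAP*

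**What the plan says.** The microbiology is in one paragraph of Methods, Clinical Procedures. Each tooth is sampled twice: from the superficial lesion before treatment, and again after removal, when "A second sample of dentin will be taken from different sites of the cavity including the walls and floor using a sterile sharp spoon excavator". Both go into the same kind of vial: "The first and second samples will be collected in screw cap sterile vials containing 1 ml of isotonic saline for microbiological evaluation". One procedure covers everyone: "dentin samples of all groups will be processed in the Advanced Techniques Laboratory in Dental research within 2 hours of collection". After vortexing, "The samples will be then regularly watered to obtain a 10^4"; in the text available the noun that should follow the number is missing. Then "a sterile loop full of sample (0.1 ml) will be collected and cultured with aseptic technique onto blood agar plates (Schaedler agar) by streaking method". After incubation "the total viable count (TVC) will be obtained and expressed as colony forming units" per ml.

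The paragraph names no second dilution level, replicate plate, countable range, detection limit or rule for a plate without colonies. The Statistical Analysis section offers paired and independent t-tests, or the signed-rank and Mann-Whitney tests for non-normal data, and does not mention zeros or ties. Objective 1 compares the methods "in decreasing the cariogenic bacteria in dentine caries of primary molar teeth in vivo", and this count is the only measure described for it.

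**The concern.** The untreated lesion and the cleaned cavity should differ widely in bacterial load, yet the same dilution is described for both. A dilution that suits heavy untreated caries may be too strong for the cleaned cavity, which is where the methods are compared. If post-removal plates read zero in both members of a pair, the pair is tied on the post-removal count and carries no information about it. If the analysis uses the reduction instead, the reduction simply equals the first count. A finding of no difference in efficacy could then not be told apart from an assay floor.

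Streaking raises a second issue. It spreads the inoculum unevenly so as to isolate colonies, and the dense part of the track is poorly suited to a CFU/ml figure.

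**Working it through.** **Inputs from the plan.** Suspension 1 ml; dilution 10^4 (read as 1:10,000); plated volume 0.1 ml; 30 teeth in each test group, each with a contralateral drilled tooth, hence 30 pairs per agent; "The level of significance will be set at 0.05", taken as two-sided. The plan states no CFU-per-colony figure or detection limit, so there is none to reproduce. Its sample size of 30 per group was set for a FLACC score and does not bear on the bacterial count.

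**Inputs that are assumptions.** Residual loads (lognormal), their SD on the log10 scale, Poisson colony counts, and no correlation between the two teeth of a child. The documents give no value for any of these, so a range is shown.

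**Step 1, value of one colony.** Dilution factor / plated volume = 10^4 / 0.1 = 100,000 CFU/ml.

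**Step 2, chance of an empty plate.** With C the true CFU/ml in the vial, P(0) = exp(-C x 0.1 / 10^4) = exp(-C / 10^5).

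- C = 10^3: exp(-0.01) = 0.990
- C = 10^4: exp(-0.1) = 0.905
- C = 10^5: exp(-1) = 0.368
- C = 10^6: exp(-10), below 0.001

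P(0) exceeds one half when C < 10^5 x ln 2 = about 69,000 CFU/ml. By the same formula, 0.1 ml plated at 10^-2 makes one colony worth 1,000 CFU/ml, and plated undiluted, 10 CFU/ml.

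**Step 3, power for a true tenfold difference after removal.** Simulation of 30 pairs, signed-rank test on CFU differences with tied pairs dropped. Each cell gives the fixed 10^-4 plate v serial dilutions.

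| Assumed medians, CFU/ml | log10 SD 1.0 | log10 SD 0.5 |
|---|---|---|
| 10^4 v 10^3 | 44% v 90% | 18% v 100% |
| 10^5 v 10^4 | 80% v 90% | 99% v 100% |
| 10^6 v 10^5 | 88% v 90% | 100% v 100% |

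The top row is sensitive to how the p-value is computed, because few pairs remain informative. At SD 1.0 about 75% and 93% of plates are empty, so both plates of a pair are empty with probability 0.75 x 0.93 = 0.70, leaving about 30 x 0.30 = 9 pairs. At SD 0.5 the figures are 85% and 98%: 0.85 x 0.98 = 0.83, leaving about 30 x 0.17 = 5 pairs. With 5 pairs the smallest exact two-sided p-value is 2 / 2^5 = 0.0625, which cannot reach 0.05. Large-sample p-values give about 51% and 39% in place of 44% and 18%. The pattern is the same.

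**Step 4, Brix3000 v Carie-Care.** These are different children, so Mann-Whitney, 30 v 30, SD 0.5, plate at 10^-4 v plate at 10^-2: medians 10^3 v 10^4, 49% v 100%; 10^4 v 10^5, 99% v 100%; 10^5 v 10^6, 100% at both. For a threefold difference, 10^3 v 3 x 10^3, 4% v 85%.

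**The case against.** A reader might infer that every sample is certain to be read at a single 1:10,000 dilution, and that post-removal plates will mostly be empty whatever the method. The documents support neither.

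- **The dilution.** The phrase is incomplete, and the odd wording before the number may be a rendering of serial dilution. Intermediate tubes may then exist, although plating them is not described. What stands is that only one dilution is described, and that CFU/ml cannot be computed without a clear factor.
- **The loads.** Mostly empty plates in every group need residual loads below about 7 x 10^4 CFU/ml in every group. The plan gives no expected count and no amount of dentin per sample. Its Research Limitations section concedes that the chemo-mechanical methods do not clear caries completely, so near-sterile cavities cannot be presumed. With median loads of 10^5 CFU/ml or more in both groups, a tenfold difference is found almost as often as with serial dilutions. This objection stands and makes the loss conditional.
- **Streaking.** Near-empty plates are not confluent, so this point cannot be added to the zero-count argument for post-removal samples. It remains for the heavy first samples, unquantified.
- **Countable range.** The plan gives none. Plates with few colonies still carry rank information, so the argument here rests on empty plates alone.

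**Conclusion.** The point holds as a conditional loss of sensitivity. On the natural reading of the paragraph, one colony equals 10^5 CFU/ml on the only measure described for objective 1, and nothing says how results below that are handled. For a true tenfold difference the effect on power runs from severe (44% v 90%, or 18% v 100%, at 10^4 v 10^3) to negligible (88% v 90%, or 100% v 100%, at 10^6 v 10^5). Which applies depends on residual loads and an SD that the documents do not give, and on reading the incomplete 10^4 as a dilution factor. It would go too far to say that the efficacy comparison is bound to fail.

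The change should be made, with medium confidence in its importance. It is cheap, and counts lost below the floor cannot be recovered once samples are discarded.

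**What to change.** Replace the dilution and streaking sentence in Clinical Procedures with text to this effect:

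*Measured 0.1 ml volumes will be spread-plated at more than one tenfold dilution: lower dilutions for the post-removal sample (for example undiluted to 10^-2) and higher ones for the first sample (for example 10^-2 to 10^-4). CFU/ml will be computed from the plate in the stated countable range, using the recorded dilution factor.*

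The exact ladder is for the laboratory to set; a few pilot samples would show where post-removal loads lie. State the countable range and the detection limit. In Statistical Analysis, state how counts below the limit enter the signed-rank and Mann-Whitney tests, for example as tied at the lowest rank, and report how many there are in each group.

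Cost: 120 teeth x 2 = 240 samples, so one or two extra plates per sample means about 240 to 480 more plates and the bench time to count them. No extra patients, visits or staff are needed.
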